### **1.6.3 Exploratory Objectives and Exploratory Outcome Measures (Research Only)**

#### **Exploratory objectives and exploratory outcomes**

- To assess the effects of ALK-001 on retinal anatomy
  - Evaluation of photoreceptors and RPE layers on SD-OCT imaging. Specifically, evaluation of RPE, ellipsoid zone (EZ) band (also known as IS/OS junction layer) and outer nuclear layer (ONL)
- To assess the effects of ALK-001 on retinal function:
  - Changes in retinal sensitivity as measured by fundus-tracking microperimetry
- Effects of ALK-001 on drusen characteristics
  - Changes in drusen volume as measured by SD-OCT
- Effects of ALK-001 on the incidence of CNV in eyes with GA, when the fellow eye has intermediate AMD
  - Incidence of CNV in eyes with GA, as assessed by PI using standard of care (FA, OCT, CFP, OCTA or combination)
- Effects of ALK-001 on the incidence of advanced AMD (CNV or GA), when the fellow eye has intermediate AMD
  - Incidence of advanced AMD in the fellow eye, as assessed by PI
- Effects of ALK-001 on the incidence of GA in eyes with CNV, when the fellow eye has GA
  - Incidence of GA in eyes with CNV, as assessed by PI
- Distance of Preferred Retinal Locus (PRL) to foveal center and other fixation characteristics
  - Changes in fixation characteristics as measured by fundus-tracking microperimetry
- Association between ALK-001 treatment effects and genetics
  - Stratification of effect size by mutations on a panel of genes
- Association between ALK-001 treatment effects and complement
  - Stratification of effect size based on subject's complement function and complement blood levels

## **1.7 STUDY DESIGN AND RATIONALE**

### **1.7.1 Overview of Trial Design**

This is a randomized, double-masked, parallel-group, multicenter study evaluating the safety and efficacy of ALK-001 in subjects with GA secondary to AMD. Approximately 300 subjects who match all eligibility criteria will be randomized to receive either ALK-001 (n = 200) at 14 mg/day or placebo (n = 100) for 24 months in a 2:1 drug:placebo ratio. After 24 months of treatment, an optional open label extension is planned to determine the lowest chronic dose that can maintain approximately 80% of deuterated vitamin A in plasma.

[figure not shown]
The expected total duration of the study from first patient first visit to last patient last visit, excluding the optional open label extension is 2 years and 9 months, which includes a total of up to 2 years of treatment with the study drug and 9 months of enrollment. Subjects, investigators and study team, and sponsor staff who may be in contact with investigators or subjects, will be masked for the duration of the study.

Safety and tolerability will be assessed by monitoring AEs, clinical laboratory tests, vital signs, ECG and physical examinations. The primary endpoint for assessment of efficacy is the growth rate of GA lesions

measured on FAF imaging and confirmed by OCT, between baseline and 24 months of treatment. Secondary efficacy endpoints include effects of ALK-001 on visual and ocular function and anatomy, as measured by questionnaires, BCVA, reading speed, and OCT. Exploratory outcomes measure include microperimetry and assessment of complement in the blood.

Protocol waivers or planned deviations may be allowed upon approval by sponsor and IRB when necessary. In certain cases, FDA review may be required, in which case such planned deviations or protocol waivers may be implemented only after receiving confirmation by sponsor that the FDA review period has been completed. Protocol waivers or deviations intended to eliminate an apparent immediate hazard to human subjects may be implemented immediately, provided that sponsor and IRB are subsequently notified, as required.

To the extent allowed in specific sections of this protocol, approvable exceptions may be granted by sponsor. Adherence to the study design requirements is essential and required for study conduct. Subject's health will be monitored through the end of the study. An independent Safety Monitoring Committee (SMC) will be commissioned to review unmasked safety data. All assessments will be performed according to the Events Table (1.2). A diagram of the study design and timelines is provided below.

## 1.7.2 Study Design Rationale

The study is designed to generate long-term safety and efficacy data of ALK-001 in subjects with GA secondary to AMD and otherwise deemed healthy to participate in the study.

### 1.7.2.1 Study Population

The study population comprises subjects 60 years old and over at the time of screening or at randomization, who are treatment-naïve to ALK-001 and have been diagnosed with geographic atrophy secondary to age-related macular degeneration in at least one eye. Subjects should be healthy otherwise, although benign conditions are acceptable if they are not likely to affect the subject's health, interact with the treatment, or confound the evaluation of safety, tolerability, or effects of ALK-001.

### 1.7.2.2 Dose Levels

A high percentage of deuterated vitamin A is recommended to demonstrate efficacy: ALK-001 is designed to replace normal vitamin A. The greater this replacement in the retina, the more efficacious ALK-001 will be at slowing the dimerization of vitamin A. Because measuring vitamin A in the retina is not directly accessible, an adult swine model has been used to demonstrate that the percentage of deuterated vitamin A in plasma mirrors that of the retina [16]. Thus, the percentage of deuterated vitamin A in plasma can be used as an indirect measure of the percentage of deuterated vitamin A in the retina.

Greater than 80% replacement of vitamin A with deuterated vitamin A is achievable: The percentage of *deuterated vitamin A* should preferably be over 80%, so that most vitamin A is in the deuterated form during the study. In mice models, ALK-001 prevented age-related declines in retinal function when as little as  $\approx$  80% of the vitamin pool was deuterated vitamin A (ALK-001's active metabolite) [70]. Eighty percent deuterated vitamin A resulted in greater than  $\approx$  4-fold reduction in the rate of dimerization. Phase 1 and Phase 2 clinical data indicate that once-daily intake of 14 mg of ALK-001 is sufficient to replace 80% of deuterated plasma vitamin A in humans after 4 weeks of treatment, with no major dietary restrictions (no liver, no vitamin A-containing supplements). Because a high percentage of deuterated vitamin A was achieved in plasma, it is unlikely that there would be a higher benefit from using a higher dose. As such, only one dose is being tested in this study.

At the dose level proposed in this study, the total intake of vitamin A (combining natural vitamin A from dietary sources + ALK-001 dose) is expected to be safe and well-tolerated for the 2-year treatment period: Daily intakes of vitamin A of  $\sim$ 100 mg (300,000 IU) for 1 year followed by  $\sim$ 50 mg (150,000 IU) during the second year were well-tolerated in a phase 3 cancer clinical trial enrolling close to 1,300 patients aged 23 to 83 years old [82] although some grade 3 and 4 toxic adverse events were observed. The degree of tolerability is usually higher in cancer trials. In another trial, daily dosing of 129 patients with sun-damaged skin for up to one year at doses up to  $\sim$ 25 mg (75,000 IU) of vitamin A has showed acceptable tolerability [72], while doses below  $\sim$ 8 mg (25,000 IU) have been shown to be relatively safe for decades [83]. Other trials testing vitamin A include a breast cancer trial testing  $\sim$ 100 mg per day (300,000 IU) for up to 2 years [84].

In an ongoing Phase 2 study, a daily administration of ALK-001 was well-tolerated, with no unexpected adverse reactions. It is important to note that vitamin A-related adverse reactions are known to resolve upon discontinuation. As such, if during the study any patient experiences signs or symptoms of hypervitaminosis A, which would place the patient at risk of continuing the study, such patient shall temporarily interrupt the study drug. See section [1.5.8.1](#) for details.

In the present study, we propose to assess the safety in patients older than 60 years old of daily intake of ALK-001 for a period of 24 months, and its efficacy on the growth rate of GA lesions. After 24 months, lower chronic doses may be assessed to determine the lowest dose that maintains  $\sim$ 80% deuterated vitamin A in plasma.

#### *1.7.2.3 Treatment Groups*

Subjects will be randomized to placebo or to ALK-001 at 14 mg/day.

Based on all mechanistic, preclinical and clinical information available to date, the chosen dose is likely to be therapeutic, as it will replace over 80% of vitamin A with deuterated vitamin A, which would be expected to slow the dimerization process over 2-fold in the retina. For percentages around 90% of replacement, dimerization is slowed 4-5 fold.

Considering the safety data to date, there is little scientific reason to explore a lower dose in the initial treatment period of 2 years, as it would increase the chance of missing a treatment benefit (type II error) without increasing the study safety in a meaningful way.

#### *1.7.2.4 Route of delivery, frequency & time of dosage*

*Oral route preferred for ALK-001:* The oral route is preferred as the retina is difficult to reach with topical formulations that might also be inconvenient (eyedrops, intravitreal injections). Vitamin A on the other hand can be taken orally and is naturally transported to the retina via retinol binding proteins (RBP) at physiologically relevant and controlled levels.

*Once daily dosage preferred:* Once daily dosing is recommended in this study based on pharmacokinetic data. Subjects will be advised to take their daily capsule at the same time each day, preferably at the time they take other medications if any.

#### *1.7.2.5 Duration of Treatment*

This study is designed to evaluate the safety and tolerability profile of ALK-001 in subjects over 60, and to determine the efficacy of ALK-001 on the progression of geographic atrophy.

The initial treatment period will end when the last subject completes the last scheduled visit.

A 2-year open label extension is planned to explore chronic maintenance dosing, as well as long term efficacy in case 2 years would not be sufficient to show an effect. Subjects who complete the initial treatment period may be offered to continue treatment, with a possible interruption between the first 2 years of treatment and the start of the open-label extension. Details of the extension period may be provided in future protocol amendments.

#### *1.7.2.6 Study Control, Randomization and Masking*

To prevent or reduce bias, a placebo will be used. This is particularly important as endpoints such as best-corrected visual acuity, reading speed, microperimetry, or assessments by the study team or reading center of RPE lesion atrophy, may be influenced with bias. Placebo will also be used to assess safety and establish the type, severity and frequency of adverse events associated with the drug.

Treatment masking will be in place to further reduce bias during data collection and analysis. Randomization will ensure there is no bias in the assignment of subjects to treatment groups, and to enhance the validity of statistical comparisons across treatment groups. No stratification will be used.

Investigators, subjects and all sponsor personnel having relevant contact with the study sites will remain masked to the treatment allocation for the duration of the study. The labels on the packaging of the study drug only indicate a random medication ID (eg: "GA2746") and not the actual treatment assignment. All capsules will weigh, look, smell and taste the same unless specified otherwise by sponsor.

Unmasking of certain personnel when necessary for some data analyses, will require sponsor's approval and will be clearly documented.

#### *1.7.2.7 Safety Evaluations*

Based upon vitamin A's known safety and tolerability profile, possible AEs of interest have been identified and will be monitored during this study (see section [1.5.8.1](#)). Safety data will be acquired by: 12-lead ECG, physical exam, ocular exams, retinal photographs, clinical laboratory tests, bioanalytical tests (vitamin A), BCVA.

To make sure that any potential for hypervitaminosis A is detected, *symptoms* such as headaches, nausea, dry lips, dry skin, *signs* such as papilledema (optic disc swelling), and clinically meaningful abnormalities

in clinical laboratories will be explored (see section 1.16.1.6). In addition, levels of retinol, retinoic acid, and retinyl esters will be measured periodically. In order to avoid study unmasking, such data will be reviewed by the SMC. See section below on pharmacokinetic evaluations.

Vitamin A-related adverse reactions are usually reversible upon discontinuation of the vitamin.

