## 1.5.8 Possible Risks and Benefits to Human Subjects

### 1.5.8.1 Possible Risks

- **Clinical laboratory results:** in an ongoing 2-year study assessing ALK-001 at a dose similar to the dose tested in this protocol, there were no reports of clinically-significant abnormal laboratory values, including for the enzyme levels and lipids listed below. Nonetheless, vitamin A has previously been associated with mild increases in the following blood parameters, which will be monitored for abnormalities and assessed for clinical significance (see 1.16):
  - *Enzyme levels:* ALT, AST and Alkaline Phosphatase.
  - *Lipids:* total cholesterol, triglycerides, HDL or LDL.
- **Side effects and toxicity:** Based on safety data acquired to date, adverse reactions due to ALK-001 at the proposed dose are expected to be rare in this 2-year study. The following side effects, associated with chronic vitamin A intake, may be reported by patients, although it is unlikely that such non-specific side effects would be associated with the study treatment in case they are reported within the first ~6 months of treatment.
  - Dermatological symptoms including dryness, desquamation or itching.
  - Alopecia, although this is not uncommon in the elderly.
  - Papilledema (optic disc swelling or fuzzy borders), with or without signs of headaches, intracranial hypertension (pseudotumor cerebri), transient visual obscurations (TVO), reports of a more noticeable or larger blind spot, transient nausea, stiff neck, dry skin or lips. Obese female subjects may be more sensitive to vitamin A.
  - Hepatomegaly, sometimes with splenomegaly
  - Other side effects related to chronic vitamin A intake may include: blurred vision, diplopia, anorexia, loss of appetite, nausea, fatigue, cheilitis, angular stomatitis, gingivitis, glossitis, conjunctivitis, peeling, epistaxis (nose bleed), pain of the bones, muscle stiffness, dysuria, exanthema, fever, vertigo, sleep disturbance, edema and swelling.
  - Vitamin A-related side effects or adverse reactions are known to resolve upon discontinuation of vitamin A treatment: therefore, if subjects present with non-tolerable adverse reactions, signs of toxicity, or symptoms which in the opinion of the investigator or sponsor may affect the health of the subjects, these subjects may be asked to temporarily interrupt the study treatment until resolution of the AE or decision to resume treatment (section 1.14.4).

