#### *1.16.1.1 Collection and Documentation of Adverse Events*

Collection of AE should occur according to the events table (Section [1.2](#)). During all instances of communication with subject, including phone calls or other forms of communication, study staff shall inquire about health-related concerns through non-directive, non-leading questions. Examples of non-directive questions include the following:

“How have you felt since your last visit / since we last spoke?”

“Have you had any new concerns or changes in your health since you were last here / since we last spoke?”

Study team should then determine if such concerns are AEs and if so list AEs on the AE log, and PI should determine if an unscheduled safety visit or a referral to a different physician is warranted (See section [1.12.12](#)). AE or health-related concerns may also be spontaneously reported by subjects between visits or during visits while undergoing physical or ocular examination, ECG, blood draw, or other assessments.

Follow-up monitoring of AEs: Study team should follow each AE until the event has resolved to baseline grade or better, the event is assessed as stable, the patient is lost to follow-up, or the patient withdraws

consent. Every effort should be made to follow all AEs or SAEs considered to be possibly-related or related to study drug, until a final outcome can be determined. After a subject discontinues participation, study team should follow AEs according to [1.16.1.5](#).

**Documentation of AE:** Information on AEs should be documented in source documents, with sufficient details and notes to allow adequate understanding of the AE dates, status, clinical diagnosis, signs, symptoms, body part involved.

**Recording and updates:** Study team shall avoid colloquialisms and abbreviations in the AE description. Not all information regarding the AE may be available at the time the AE is detected or documented (including for example: definitive diagnosis, dates of AE, AE outcome, action taken, or causality to study treatment). Such information should be recorded as soon as it becomes available. See section [1.16](#) for details.

**Description of the event:** When recording AEs, study team should use correct medical terminology and concepts. AEs may fit into different categories based on available information:

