**Definitive diagnosis:** If a clinical diagnosis is known and confirmed by investigator, record the diagnosis. Study team may also list signs and symptoms in a side “note.” (eg: record “hepatitis” if known to be the diagnosis rather than “jaundice, asterixis, and elevated transaminases”).

**Definitive diagnosis along with signs/symptoms not normally associated with the diagnosis:** If any signs or symptoms are not normally associated with the definitive diagnosis, study team shall list these signs/symptoms in separate AEs.

**Presumed/Provisional diagnosis:** If at the time of report, a diagnosis is unknown or unsure, study team shall record in a single AE, the provisional diagnosis as well as the reported signs/symptoms (eg: “presumed influenza with low grade fever”). If a clinical diagnosis becomes later known and confirmed by investigator, AE should be updated to indicate the definitive diagnosis.

**Constellation of signs or symptoms that cannot be characterized as a single diagnosis:** study team shall record each individual sign and/or symptom as its own event. These AEs should be updated if a diagnosis is later determined

**AEs occurring secondary to a primary event:** in general, in case of a cascade of events or clinical sequelae, study team shall record the primary cause, with the exception of severe or serious secondary events, or medically significant AEs occurring at separate points in time, which shall be recorded separately. For example:

- *If vomiting results in mild dehydration with no additional treatment, only vomiting should be recorded.*
- *If vomiting results in severe dehydration, both events should be recorded separately*
- *If dizziness leads to a fall and consequent fracture, all three events should be recorded separately*

**Recording of AE Parameters:** For each AE, study team should record:

- Verbatim description of the event (including either *definitive* diagnosis with signs/symptoms in notes, or a *provisional* diagnosis, along with signs and symptoms in the verbatim description, when a definitive diagnosis is not known)
- Start Date/Time
- Is the AE ongoing or not?
- End Date/Time
- Is the AE “serious” or “not serious” (see section [1.16.3](#))
- AE severity (see section [1.16.1.11](#))

- Frequency/Pattern (Single event, Intermittent, continuous)
- Action taken related with study treatment (see section 1.16.1.13)
- Action taken unrelated with study treatment (see section 1.16.1.15)

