7.2. Adverse Events and Serious Adverse events

All reported adverse events (AEs) will be coded using MedDRA version 22.0 or higher following the MedDRA Term Selections Points to Consider.

An AE will be considered a treatment-emergent adverse event (TEAE) if it starts on or after the reference start date or if it starts before the reference start date but worsens on or after the reference start date, up to 28 days after last study drug administration.

The overall summary of TEAEs by treatment arm will include the numbers and percentages of subjects with at least one TEAE in the following categories:

- Any TEAE
- TEAE by Maximum Severity (evaluated by the investigator as Mild, Moderate and Severe)
- TEAE related to study drug (evaluated by the investigator as definitely, possibly, probably related)
- Treatment-emergent SAE
- Treatment-emergent SAE related to study drug (evaluated by the investigator as definitely, possibly, probably related)
- TEAE leading to study drug discontinuation
- TEAE leading to study drug interruption
- TEAE leading to study discontinuation
- TEAE leading to death (outcome = “Fatal”)

In addition, the numbers and percentages of subjects with at least one TEAE will be summarized by system organ class (SOC) and preferred term (PT) for the following categories:

- Any TEAE

- TEAE by Maximum Severity (evaluated by the investigator as Mild, Moderate, and Severe)
- TEAE related to study drug (evaluated by the investigator as definitely, possibly, probably related)
- Treatment-emergent SAE
- Treatment-emergent SAE related to study drug (evaluated by the investigator as definitely, possibly, probably related)
- TEAE leading to study drug discontinuation
- TEAE leading to study drug interruption
- TEAE leading to study discontinuation
- TEAE leading to death (outcome = “Fatal”)

Subjects who experienced multiple AEs within the same SOC or PT will only be counted once for that SOC or PT for that level of summarization. The maximum severity will be used in the summary of “TEAE by maximum severity” for subjects who experienced multiple AEs within the same SOC/PT.

Common TEAEs with at least 5% subjects in treatment group ALK-001 or with at least 2% subjects in treatment group ALK-001 and greater than placebo in percentage, will be summarized by PT respectively.

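### The protocol names vitamin A adverse events of interest, but SAP 7.2 has no grouped summary of subjects with at least one of them

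*Protocol*

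**What the plan says.** Protocol v1.1, on which the SAP is based, sets the aim in section 1.7.2.7. From vitamin A's known profile, "possible AEs of interest have been identified and will be monitored during this study". The purpose follows: "To make sure that any potential for hypervitaminosis A is detected", by looking at symptoms (headache, nausea, dry lips, dry skin), signs (papilledema), laboratory abnormalities and retinoid levels. It refers to section 1.5.8.1, where the list is introduced with "The following side effects, associated with chronic vitamin A intake, may be reported by patients". That list runs to roughly 30 effects across several body systems, starting with "Dermatological symptoms including dryness, desquamation or itching" and going on to alopecia, papilledema and intracranial hypertension, hepatomegaly, cheilitis, fatigue, fever, vertigo and others.

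Section 1.16.1.1 governs how these reach the database. On elicitation, "study staff shall inquire about health-related concerns through non-directive, non-leading questions". When a constellation of symptoms has no single diagnosis, "study team shall record each individual sign and/or symptom as its own event".

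SAP 7.2 counts subjects with any TEAE, by maximum severity, related, serious, and leading to interruption, discontinuation or death, then repeats these by system organ class and preferred term. It adds a common-event display by preferred term ("Common TEAEs with at least 5% subjects in treatment group ALK-001", or at least 2% and above placebo) and a display by preferred term of time to first occurrence. It has no adverse-event-of-interest category. SAP 7.0 plans no formal safety testing.

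**The concern.** Vitamin A excess is a syndrome: one subject has dry lips, another peeling skin, another headache. Recorded as separate events, these fall under several preferred terms and system organ classes, each with few subjects. The natural measure is the number of subjects with any of them, and it cannot be obtained by adding preferred-term rows because the same subject may appear in several. Someone could rebuild the count from the subject listings, but the choice of terms would then be made with the results in view. At stake is how clearly the tables can show, or credibly rule out, an excess of the clinical events that the protocol itself singled out.

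**Working it through.** The documents state no rate, count or detection probability for these events, so there is no figure to reproduce. What follows is illustration on assumed rates.

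**Inputs.** SAP 3.1: 200 subjects randomized 2:1, so about 200 × 2/3 = 133 on ALK-001 and 67 on placebo (arm counts are not stated). Assumed rate per term: 2% placebo, 5% ALK-001. Yardstick: exact power of Fisher's test, nominal two-sided 0.05, excess on ALK-001. As no safety test is planned, this only measures how distinguishable the arms would be.

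**One preferred term, 2% v 5%.** Power 6.3%. The chance that at least one of k independent terms reaches p<0.05 is 1 − (1 − 0.0634)^k: 32% for k = 6, 41% for 8, 48% for 10, with no control for multiplicity.

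**Display rule.** At least 2% of 133 means 3 subjects. A 2% v 5% term enters the table of terms at 2% and above placebo with probability 89%. A term at 2% in both arms enters it with probability 38%. Terms are shown but not well separated from noise.

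**System organ class row.** Three such terms in one class, with unrelated background b: rate = 1 − (1 − p)^3 × (1 − b).

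| b | Placebo v ALK-001 | Power |
|---|---|---|
| 0 | 5.9% v 14.3% | 36% |
| 10% | 15.3% v 22.8% | 20% |
| 20% | 24.7% v 31.4% | 14% |

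**Group of k independent terms, all raised.** Rate = 1 − (1 − p)^k.

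| k | Placebo v ALK-001 | Power |
|---|---|---|
| 6 | 11.4% v 26.5% | 68% |
| 8 | 14.9% v 33.7% | 81% |
| 10 | 18.3% v 40.1% | 87% |

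Over 6 to 12 terms and 1-5% v 3-8% per term, the group has 39-92% and a single term 1-7%.

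**Clustering.** Suppose the same term rates arise only in a susceptible share s of each arm. The rate within that share is q = 0.02/s on placebo, and the group rate is s × [1 − (1 − q)^k].
- s = 5% v 12.5%, q = 0.40, k = 6: 4.8% v 11.9%, power 30%.
- s = 8% v 20%, q = 0.25, k = 6: 6.6% v 16.4%, power 46%.
- s = 8% v 20%, k = 10: 7.5% v 18.9%, power 54%.
- Upper limit for s = 8% v 20% (every susceptible subject has an event): power 58%.

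**Pooling all listed effects.** Take 30 independent terms at 2% background, of which r rise to 5%. Placebo: 1 − 0.98^30 = 45.5%.
- r = 6: 1 − 0.98^24 × 0.95^6 = 54.7%, power 20%.
- r = 8: 1 − 0.98^22 × 0.95^8 = 57.5%, power 32%.

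A long list thus loses most of the gain, which is why the list must be short.

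**The case against.** Section 1.7.2.7 promises monitoring and exploration, not a composite table, and the Safety Monitoring Committee reviews safety data at least yearly with access to unmasked data. Much of the profile does not depend on adverse-event terms. SAP 7.3 summarises liver tests by threshold and plots ALT, AST, bilirubin, triglycerides, HDL and LDL. SAP 8.0 summarises retinoid concentrations by arm and visit. The overall row for drug-related TEAEs is a subject-level count across all terms, protocol 1.16.1.12 asks the investigator to weigh known associations with similar treatments, and SAP 4.6.4 imputes missing causality as definitely related. The time-of-onset table partly gives the later-onset view.

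Most of this stands. A reader might infer that the SAP shows only single preferred terms, that no row could reveal an excess, or that the protocol's safety aim is not delivered. The documents support none of these, because the system organ class, any-event and related-event rows exist and the laboratory and exposure parts are covered.

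Three limits remain. The related row rests on attribution, and section 1.5.8.1 says that such effects are unlikely to be drug-associated within about the first 6 months. System organ class rows mix in unrelated events. SAP 7.7 grades ocular findings only as normal or abnormal with or without clinical significance, so that table does not identify papilledema.

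**Conclusion.** The point holds as a gap between the two documents: a named set of clinical events with a stated detection aim has no matching grouped summary. The planned tables do not give the number of subjects per arm with at least one such event. It is a worthwhile, low-cost improvement, not a failure of the safety analysis.

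Its size cannot be fixed from the documents. The contrast of 6% for one term against 68-87% for six to ten grouped terms is tempting to quote as the loss, but it needs assumed rates, independent terms and every term raised, and it sets one term against the group. At least one of six to ten terms would reach nominal significance 32-48% of the time, and clustering or a long list removes much of the advantage. The direction is sound for a short, specific list; the amount is illustrative only.

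**What to change.** In SAP 7.2, before unmasking, define one grouped category of potential hypervitaminosis A events with a fixed MedDRA preferred-term list. Base it on the events named in protocol 1.7.2.7 (dry skin and lips, headache, nausea, papilledema) plus the more specific items of 1.5.8.1 (desquamation, cheilitis, alopecia, intracranial hypertension). Do not use the full list of about 30 largely non-specific effects.

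Report the number and percentage of subjects with at least one event by arm, with the risk difference and 95% CI, overall and for first onset after Month 6. Add two subgroups: skin/mucosal and papilledema/intracranial hypertension. Keep it descriptive, in line with SAP 7.0. Label any power figure as illustrative and state its assumptions.

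The cost is one or two extra tables and a masked judgement on which terms belong in the list. If the list is drawn up only after unmasking, the report should call the analysis post hoc.
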